5.2 Secondary Endpoints

1. Time to therapeutic colistin dosing and number of therapy interruptions due to changes in creatinine with standard colistin, modified colistin, and standard tobramycin dosing.
2. Total number of IV doses delivered over the course of APE treatment.
3. Change in sputum microbiology profile following treatment with colistin versus tobramycin.
4. Number of exacerbations in the ensuing year and time to first pulmonary exacerbation following APE treatment.
5. Absolute change in Cystic Fibrosis Questionnaire-Revised (CFQ-R) respiratory domain score before and after APE treatment.
6. Number of episodes of neurotoxicity and ototoxicity in study arms, based on case-report form.
7. Colistin peak, mid-point, and trough during APE, for calculations of area under the curve (AUC).

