6. SUBJECT SELECTION

6.1 Study population

Subjects with a diagnosis of CF who meet all the inclusion and none of the exclusion criteria will be eligible for participation in this study.

6.2 Inclusion criteria:

1. Male or female \geq 18 years of age at Visit 1.
2. Documentation of CF diagnosis as evidenced by one or more clinical features consistent with the CF phenotype and one or more of the following criteria:
 - Sweat chloride equal or greater than 60 mEq/L by quantitative pilocarpine iontophoresis test.
 - Two well-characterized mutations in the CFTR gene
 - Abnormal nasal potential difference (change in NPD in response to a low chloride solution and isoproterenol of less than -5 mV).
3. Documentation of the presence of an acute pulmonary exacerbation, based on CF Foundation guidelines, as diagnosed by a faculty member of the Denver Adult CF Program.
4. Respiratory culture(s) demonstrating evidence of *Pseudomonas aeruginosa* or *Achromobacter species* airway infection.
5. Subject is able to produce sputum, undergo phlebotomy, and provide written consent.
6. The subject's treating physician has determined that they should receive either tobramycin or colistin intravenously as one of the designated agents for their APE

treatment. Subjects who are able to receive either tobramycin or colistin as part of their antibiotic regimen will be randomized into one of three arms. If a treating physician deems that a subject cannot receive tobramycin due to vestibular toxicity, ototoxicity or bacterial resistance, the subject will be randomized to either standard or PK-adjusted colistin.

6.3 Exclusion criteria:

1. Presence of chronic renal insufficiency, with abnormal baseline creatinine >1.2mg/dL.
2. Presence of a condition or abnormality that in the opinion of the investigator would compromise the safety of the patient or the quality of the data.
3. Inability to perform reproducible spirometry.
4. Inability to expectorate sputum.

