Standard tobramycin arm: Subjects receive IV tobramycin 8-10 mg/kg/day (X-gen Pharmaceuticals) with once daily dosing for 14 days. Peaks and troughs are drawn with the second dose of tobramycin, and the drug is infused over 30 minutes. Dose adjustment will occur to achieve non-detectable troughs and peaks 20-30 mg/dL². Tobramycin concentrations are assessed once weekly during each week of APE treatment.

8.4.3 Dose modification: Subjects active in the study who experience moderate to severe toxicity will undergo dose adjustments as follows. If clinical providers and site investigators believe that it is appropriate to have the subject continue in the study, this will be allowed. If study drug is discontinued, the data acquired prior to its discontinuation will be utilized in the analysis.

1. Tobramycin will be discontinued if ototoxicity occurs (patient complains of ringing in ears and/or hearing loss).
2. Tobramycin will be held with increases of creatinine >0.3 mg/dL. If creatinine increases are not reversible, the drug is discontinued. If they are reversible, the drug may be resumed at lower dosing or longer intervals, at the discretion of the physician and the clinical pharmacist in joint consultation.
3. Colistin will be discontinued for serious episodes of neurotoxicity, such as debilitating headache, seizure, and neuromuscular weakness.
4. Colistin will be held for one dose and then resumed at a lower dose if creatinine rises \geq 0.3 mg/dL from baseline. If creatinine fails to recover or continues to rise, the drug will be discontinued. Patients who do not undergo PK measurements are maintained at the highest dose achievable (between 3-5 mg/kg/day) without renal insufficiency (< 0.3 mg/dL increase in serum creatinine).

8.4.4 Study drug preparation, handling and dispensing: Appropriately trained pharmacy personnel and nursing staff are responsible for the administration of medications. Medications are dispensed and labeled in accordance with federal and local state Board of Pharmacy regulations.

8.4.5 Administration instructions: Instruction of hours of administration, dose, and duration of administration will be transmitted from the National Jewish Health | Saint Joseph Hospital inpatient pharmacists to CF pulmonary floor nursing staff. Drugs will be administered through indwelling peripherally inserted central catheters (PICC) or indwelling ports.

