9.1.3 Medical History

Relevant medical history, including history of current disease, other pertinent respiratory history, and information regarding underlying disease will be recorded at Visit 1.

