9.1.9 Adverse Events

Information regarding occurrence of adverse events will be captured throughout the study. A case report form (CRF) will be completed by the rounding physician, which will include signs and symptoms related to specific toxicities due to tobramycin or colistin. Severity, seriousness, outcome, treatment, and relation to study participation will be recorded.

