10 EVALUATIONS BY VISIT

10.1 Visit 1

1. Review the study with the subject (or subject's legal representative) and obtain written informed consent and HIPAA authorization.
2. Administer QoL questionnaire
3. Review respiratory culture results in the previous 12 months
4. Assign the subject a unique identification number.
5. Record demographics data.
6. Record medical history, including exacerbation criteria based on Rosenfeld score, baseline serum creatinine, and number of exacerbations in the preceding year.
7. Record concomitant medications.
8. Perform a complete physical examination.
9. Obtain and record vital signs.
10. Record oximetry.
11. Record results from blood and urine clinical laboratory tests (chemistry, hematology).

12. Record results from urine or blood pregnancy test (if female of child-bearing potential).
13. Record results from spirometry.
14. Record results from sputum culture microbiology.
15. Collect urine for Nephrocheck®

10.2 Visit 2

1. Administer QoL questionnaire
2. Record serum creatinine from daily clinical laboratory draws.
3. Collect urine for Nephrocheck®
4. Record urine protein from three times weekly clinical laboratory check.
5. Record tobramycin peak and trough from week 1 clinical laboratory draw
OR
Collect blood, sputum, and urine for colistin pk measurement.

10.3 Visit 3

1. Administer QoL questionnaire
2. Record serum creatinine from daily clinical laboratory draws.
3. Collect urine for Nephrocheck®
4. Record urine protein from three times weekly clinical laboratory check.
5. Record tobramycin peak and trough from week 2 clinical laboratory draw
OR
Collect blood, sputum, and urine for colistin pk measurement.

10.4 Visit 4

1. Administer QoL questionnaire.
2. Record concomitant medications.
3. Record spirometry.
4. Record serum creatinine from daily clinical laboratory draws.
5. Record results from sputum culture microbiology.
6. Record total number of IV antibiotics doses over the preceding 14 days.
7. Collect urine sample for Nephrocheck®.
8. Complete Case Report Form (for toxicities).

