11. ADVERSE EXPERIENCE REPORTING AND DOCUMENTATION

11.1 Adverse Events

An adverse event (AE) is any untoward medical occurrence in a clinical investigation of a patient administered a pharmaceutical product and that does not necessarily have a causal relationship with the treatment. An AE is therefore any unfavorable and unintended sign (including an abnormal laboratory finding), symptom or disease temporally associated with the administration of an approved product with experimental dosing regimen, whether or not related to that product. An unexpected AE is one of a type not identified in nature, severity or frequency in the current Prescribing or Product Information or of greater severity or frequency than expected based on the information in the Prescribing or Product Information.

The investigator will probe, via discussion with the subject, for the occurrence of AEs during each subject visit and will record the information in the site's source documents. Adverse events will be recorded in the subject CRF.

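### No toxicity-specific pre-dose record and no new-or-worsened rule, while subjects with earlier tobramycin ototoxicity or vestibular toxicity enter only the colistin arms: old complaints may be counted as colistin events

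*Combined protocol and SAP*

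**What the plan says.** **The outcome.** Section 5.2, item 6 sets a between-arm endpoint: "Number of episodes of neurotoxicity and ototoxicity in study arms, based on case-report form". Section 15.3 compares the incidence of ototoxicity, vestibular toxicity and neurotoxicity judged related to treatment, using logistic regression.

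**The form.** In section 10 the toxicity form appears only in the Visit 4 list (10.4, item 8): "Complete Case Report Form (for toxicities". Table 3 has no row for it. Section 9.1.9 says "Information regarding occurrence of adverse events will be captured throughout the study" and adds, without giving a time, "A case report form (CRF) will be completed by the rounding physician, which will include signs and symptoms related to specific toxicities". Section 11.1 says "The investigator will probe, via discussion with the subject, for the occurrence of AEs during each subject visit". Section 10.5 records adverse events at an acute or early-termination visit.

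**The baseline.** Section 9.1.3 reads: "Relevant medical history, including history of current disease, other pertinent respiratory history, and information regarding underlying disease will be recorded at Visit 1". The Visit 1 list (10.1) adds the Rosenfeld score, baseline creatinine, prior-year exacerbations and a complete physical examination. Neither place names tinnitus, hearing loss, imbalance or neurological symptoms.

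**The allocation.** Section 6.2, item 6 deals with patients whom their physician rules out for tobramycin. Its wording is: "cannot receive tobramycin due to vestibular toxicity, ototoxicity or bacterial resistance, the subject will be randomized to either standard or PK-adjusted colistin". Section 2.1 describes the same route for earlier ototoxicity or vestibular toxicity from tobramycin. It also lets subjects who cannot receive colistin be enrolled to the tobramycin arm only.

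**The concern.** An incidence comparison of symptoms needs a record of which symptoms were present before treatment. It matters most when the arms differ at entry in how many subjects carry those symptoms, and here the eligibility rule creates that difference. Some patients are kept away from tobramycin because it has already harmed their hearing or balance, and all of them go to colistin.

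If an old complaint of this kind is written on a form completed during or after treatment, it can enter the count as a colistin event. What is at stake is the colistin v tobramycin contrast on ototoxicity and vestibular toxicity, where the distortion would run against colistin. A missing pre-dose record cannot be recovered once dosing has begun.

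**Working it through.** The plan gives no expected ototoxicity rate and no share of subjects unable to receive tobramycin, so it has no figure to reproduce. The check has two parts.

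**1. The sections side by side**

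- *When the form is completed.* Section 10 says Visit 4. Sections 9.1.9 and 11.1 describe capture throughout and at each visit. These can be reconciled only if 10.4, item 8 means finishing a form already in use, and the plan does not say so.
- *Pre-dose record.* Visit 1 has a general history and a physical examination. The rule in 9.1.4 that new findings become adverse events covers abnormal physical-examination findings. Tinnitus is a reported symptom and falls outside it.
- *Other outcomes.* FEV1, CFQ-R, creatinine and the Nephrocheck urine each have a specified Visit 1 value. These symptom outcomes do not.
- *Allocation and model.* The randomisation factors (8.1) are gender, FEV1 % predicted and time of enrolment. The covariates in 15.3 are age, medications such as vancomycin, baseline FEV1, prior-year admissions, nephrotoxic antibiotic exposure over five years and CF related diabetes. Neither list includes tobramycin eligibility or prior ototoxicity or vestibular toxicity.
- *Blinding.* Section 8.2 leaves subjects and investigators unblinded to tobramycin v colistin.

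**2. Illustration of size**

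Inputs from the plan: 30 subjects per arm (15.4); two-sided 0.05 (15.2).

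Assumptions:
- p0 = 5%, the true rate of new events, equal in every arm;
- q, the share of a colistin arm enrolled there because of prior ototoxicity or vestibular toxicity;
- s, the share of those subjects whose old symptoms are written down and counted;
- no carried-over complaints in the tobramycin arm.

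Observed colistin rate: p = p0 + (1 − p0) × q × s. The tobramycin arm expects 30 × 0.05 = 1.5 events. The last column is the exact probability that a Fisher test of one colistin arm against tobramycin, 30 v 30, shows colistin significantly worse. Fisher stands in for the planned logistic model.

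| q | s | p | Events per 30, colistin v tobramycin | Odds ratio | False finding that colistin is worse |
|---|---|---|---|---|---|
| 10% | 25% | 0.05 + 0.95 × 0.025 = 7.4% | 2.2 v 1.5 | 1.5 | 0.5% |
| 20% | 50% | 0.05 + 0.95 × 0.10 = 14.5% | 4.4 v 1.5 | 3.2 | 8.3% |
| 30% | 50% | 0.05 + 0.95 × 0.15 = 19.3% | 5.8 v 1.5 | 4.5 | 21.5% |

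With no carry-over (q × s = 0), each arm expects 1.5 events and the false-finding probability is about 0.1%. If every old complaint were counted at q = 30% (s = 100%), the colistin rate would be 33.5%, with 10.1 v 1.5 events and a false-finding probability of 74.6%. That is an outer bound and takes no account of the relatedness judgement.

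**The case against.** The strongest reply is that the plan already filters old complaints. Section 11.1 defines an adverse event as temporally associated with administration. The three related categories in 11.3 refer to a reasonable time sequence from dosing. Section 15.3 analyses treatment-related events, and 5.2 counts episodes. The subjects of concern are also those whose history the physician already knows, and the general history at Visit 1 has room for it. The form itself is not in the documents, so it may carry onset dates. Section 10's lists are plainly incomplete: Table 3 requires physical examination and vital signs at Visits 2 to 4, and 10.2 to 10.4 list neither.

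Much of this stands. It makes the count of old complaints uncertain, but it does not remove the gap. The relatedness judgement is open label and would be made without a specified symptom record to compare against. The count in 5.2, item 6 carries no relatedness condition. The plan permits a record of prior ototoxicity at Visit 1 but does not require one.

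Four stronger readings are tempting and are not supported:

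- *Toxicity is assessed only at Visit 4.* Sections 9.1.9, 10.5 and 11.1 say otherwise. What the text supports is an inconsistency about the form.
- *Any long-standing complaint meets the definition of ototoxicity.* The sentence "Tobramycin will be discontinued if ototoxicity occurs (patient complains of ringing in ears and/or hearing loss" in 8.4.3 is a stopping rule for tobramycin. It does not define the endpoint.
- *Every subject who cannot receive tobramycin brings old symptoms.* Bacterial resistance is a separate reason in 6.2, item 6. The 30.4% aminoglycoside resistance figure in the Background is therefore no proxy for prior ototoxicity.
- *All the channelling runs one way.* Section 2.1 also opens a tobramycin-only route, which could carry other prior complaints into that arm. Its size is not given.

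**Conclusion.** The point holds as a gap in data collection and endpoint definition that leaves the colistin v tobramycin comparison of ototoxic and vestibular events open to bias against colistin. It does not show that such bias will occur. Under the stated assumptions the effect runs from trivial (2.2 v 1.5 events) to material (5.8 v 1.5). Those figures depend on q, s and p0, none of which the documents give, and without a pre-dose record the trial could not tell afterwards which case applied.

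The scope is limited. Standard v PK-adjusted colistin is balanced on average, because the colistin-only subjects are randomised between those two arms. Acute kidney injury, the outcome behind the sample size, has a baseline creatinine. Neurotoxicity shares the missing baseline, but the colistin-only route is not defined by prior neurotoxicity, so no direction of bias can be inferred for it.

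**What to change.** 1. Add the existing toxicity form to 10.1, to be completed before the first study-drug dose, and to 10.2 and 10.3. This is feasible, because 8.4.1 starts tobramycin or colistin on the second hospital day.
2. In 5.2, item 6 and in 15.3, define these events as new or worsened relative to the pre-dose form, with an onset date. The Kaplan-Meier analysis of neurotoxicity in 15.2 needs that date in any case.
3. State the form's timing in the same way in 9.1.9, section 10, Table 3 and 11.1.
4. Record eligibility for each drug and the reason for any restriction. Compare colistin with tobramycin on these events among subjects eligible for all three arms, or stratify by eligibility. The new-or-worsened rule removes carried-over complaints. This step also deals with any higher risk of new events in subjects with prior toxicity.

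The cost is one existing form at three more existing visits and a few lines of text. Restriction leaves fewer subjects in the colistin v tobramycin comparison. Stratification costs much the same, since a colistin-only stratum has no tobramycin subjects to compare. If q were 10% to 30%, prior toxicity alone would remove 3 to 9 of the 30 in each colistin arm, and resistance would add to that. No treatment rule changes.

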10.5 Acute Visit/Early Termination of Study Participation

1. Administer QoL questionnaire
2. Record any adverse events.
3. Review and record subject dosing for colistin or tobramycin since last visit.
4. Record changes to concomitant medications.
5. Perform complete physical examination.
6. Record vital signs.
7. Record spirometry.
8. For episodes of renal toxicity, monitor daily measures of serum creatinine for return to baseline.

11. ADVERSE EXPERIENCE REPORTING AND DOCUMENTATION

11.1 Adverse Events

An adverse event (AE) is any untoward medical occurrence in a clinical investigation of a patient administered a pharmaceutical product and that does not necessarily have a causal relationship with the treatment. An AE is therefore any unfavorable and unintended sign (including an abnormal laboratory finding), symptom or disease temporally associated with the administration of an approved product with experimental dosing regimen, whether or not related to that product. An unexpected AE is one of a type not identified in nature, severity or frequency in the current Prescribing or Product Information or of greater severity or frequency than expected based on the information in the Prescribing or Product Information.

The investigator will probe, via discussion with the subject, for the occurrence of AEs during each subject visit and will record the information in the site's source documents. Adverse events will be recorded in the subject CRF.

11.2 AE severity

The National Cancer Institute's Common Terminology Criteria for Adverse Events (CTCAE) Version 4.0, as modified for cystic fibrosis, should be used to assess and grade AE severity, including laboratory abnormalities judged to be clinically significant. If the experience is not covered in the modified criteria, the guidelines shown in Table 4 below should be used to grade severity. It should be pointed out that the term "severe" is a measure of intensity and that a severe AE is not necessarily serious.

Table 4. AE Severity Grading

Severity (Toxicity Grade)	Description
Mild (1)	Mild; asymptomatic or mild symptoms; clinical or diagnostic observations only; intervention not indicated.
Moderate (2)	Moderate; minimal, local or noninvasive intervention indicated; limiting age-appropriate Instrumental activities of daily living (e.g. preparing meals, using the telephone, managing money)
Severe (3)	Severe or medically significant but not immediately life threatening; hospitalization or prolongation of hospitalization indicated; disabling; limiting self care activities of daily living (e.g., bathing, dressing, feeding self, using toilet, taking medications)
Life-threatening (4)	Life-threatening consequences; urgent intervention indicated.
Death (5)	Death related to AE.

11.3 AE Relationship to Study Drug

The relationship of an AE to the study drug should be assessed using the following guidelines in Table 5.

Table 5. AE Relationship to Study Drug

Relationship to Drug	Comment
Definitely	Previously known toxicity of agent; or an event that follows a reasonable temporal sequence from administration of the drug; that follows a known or expected response pattern to the suspected drug; that is confirmed by stopping or reducing the dosage of the drug; and that is not explained by any other reasonable hypothesis.
Probably	An event that follows a reasonable temporal sequence from administration of the drug; that follows a known or expected response pattern to the suspected drug; that is confirmed by stopping or reducing the dosage of the drug; and that is unlikely to be explained by the known characteristics of the subject' clinical state or by other interventions
Possibly	An event that follows a reasonable temporal sequence from administration of the drug; that follows a known or expected response pattern to that suspected drug; but that could readily have been produced by a number of other factors.
Unrelated	An event that can be determined with certainty to have no relationship to the study drug.

11.4 Serious Adverse Experiences (SAE)

An SAE is defined as any AE occurring at any dose that results in any of the following outcomes:

- Death
- A life threatening adverse experience
- Prolongation of existing hospitalization
- A persistent or significant disability/incapacity
- A congenital anomaly/birth defect

Other important medical events may also be considered an SAE when, based on appropriate medical judgment, they jeopardize the subject or require intervention to prevent one of the outcomes listed.

11.4.1 Serious adverse experience reporting

The coordinator will document all SAEs that occur (whether or not related to study drug) on an SAE Report Form. The collection period for all SAEs will begin after informed consent is obtained and end after procedures for the final study visit have been completed.

All SAE Report forms will be reviewed by the site investigator and sent to the Medical Monitor within one business day of the site learning of the event.

The site will notify the Medical Monitor of additional information or follow-up to an initial SAE Report as soon as relevant information is available. Follow-up information is reported on an SAE Report Form.

In accordance with the standard operating procedures and policies of the local Institutional Review Board (IRB)/Independent Ethics Committee (IEC), the site investigator will report SAEs to the IRB/IEC.

